CALCIFYING TENDINOPATHY OF THE ROTATOR CUFF: BARBOTAGE VS SHOCK WAVES

BOTCH (5775)

19/6/24

PROYECT BOTCH

RESEARCH PROJECT – BOTCH (5775) - Version 3 (19/06/2024)

CALCIFYING TENDINOPATHY OF THE ROTATOR CUFF: BARBOTAGE Vs SHOCK WAVES

DEPARTMENT: PHYSICAL MEDICINE AND REHABILITATION

1. Starting assumptions

Calcifying tendinitis (CT) of the rotator cuff is one of the most common pathologies in the clinical practice of Med. Physical Medicine and Rehabilitation. It is based on the accumulation of calcium hydroxyapatite, causing inflammation, pain and functional impotence.

The use of ultrasound in consultation has favored the diagnosis, classification and treatment in some cases. Regarding their classification, they are classified in 3 grades according to Bianchi Martinoli's classification.

For their treatment, rest, anti-inflammatory drugs (NSAIDs) and kinesitherapy are the first-line treatments. But in resistant cases, other therapies such as extracorporeal shock waves (ESWT) and or ultrasound-guided barbotage (US-PICT).

Currently, the use of these last two therapies tends to have better results in ultrasound types II and III. However, the results obtained with each treatment have not been compared.

Given the current situation regarding waiting times, knowing in which cases one or the other therapy should be indicated is very useful in order to avoid overloading the system and to give the patient the best possible treatment in the shortest possible time.

Starting hypothesis: Patients with CT, in its different degrees, who have received US-PICT as treatment, obtain the same VAS differences at 1 month, 3 months and 6 months as patients who received ESWT as treatment in the population.

2. Background and previous results

Shoulder pain is a very frequent complaint among adults. A large number of these are due to TC with prevalences close to 8%, especially in women aged 30 - 60 years (1).

Of the risk factors that we can assume, many consider that "hormonal abnormalities and/or autoimmune diseases such as hypothyroidism, diabetes mellitus and rheumatoid arthritis" (2) play an important role in the development and chronicity of TC (3).

The natural course of CT pathogenesis is currently incomplete. As discussed in the starting hypothesis, calcium hydroxyapatite deposition is the pathophysiological basis of CT. This deposit, as opposed to the first theories that described its appearance due to tendon degeneration, is not currently supported (4).

In this pathology, what is known is the evolutionary course passing through 3 phases according to Uhthoff et al: (5)

1. Pre-calcified → 2. Calcified (edema and pain) → 3. Post-calcification

For diagnosis, physical examination and imaging-based tests are strictly enforced and among them, radiography and ultrasound of the rotator cuff are the gold standard tests. Thanks to the use of these tests, two classifications have been created that relate to the evolutionary course described above.

Radiological classification by Gärtner and Heyer (6)

1. Circumscribed, dense, in formation.
2. Dense/translucent, circumscribed/cottony outline
3. Cloud-like and translucent, in resorptive phase.

Ultrasound classification by Bianchi Martinoli (7)

1. Type I: hyperechoic foci with good acoustic shadowing.
2. Type II: hyperechoic foci with a slight acoustic shadowing.
3. Type III: isoechoic with tendon, without acoustic shadowing.

The symptomatology of this disease has great variability among patients. If we speak of general numbers, 50% of the patients recover spontaneously or following conservative guidelines in the first 3 months and 20% during the first year. The remaining 30% develop repeated pain for months in periods exceeding several years (8).

Having explained the most relevant data on which CT is based, we focus on treatment. The initial therapy, being a self-limited disease, is focused on symptomatology control with anti-inflammatory drugs and oral analgesics, being able to resort to glucocorticoid injections in the rotator cuff in those cases in which inflammation is observed. As explained above, there is a large percentage of patients whose CT is limited, but the question is what about the remaining 50%? It is in these patients, with CT refractory to treatment, where therapies such as ESWT or US-PICT appear.

The use of ESWT has been for many years a controversial practice in relation to its use in CT due to the lack of studies. Following the study published by Gerdesmeyer et al, in which it was shown that even with low energy ESWT it was possible to dissolve these calcifications (9), its use and new publications have been encouraged.

All deriving in 2016, when the SETOC (Spanish Society of Shock Wave Treatments), was able to include CT as an approved standard indication for the use of high energy ESWT.(10).

Regarding the use of US-PICT, there are multiple studies that support this practice. They recognize it as "an effective and safe treatment in CT, since it produces a significant clinical and radiological improvement"(7). A study carried out in the year 2022, which retrospectively sought to study the results of this technique, culminated demonstrating a significant improvement in pain in patients treated with this technique (11).

Few studies have been conducted to determine which type of therapy is most effective in each case, with very mixed conclusions. In the 2014 systemic review by Louwerens et al, it was shown that both the use of high-energy ESWT and US-PICT are effective treatments in chronic cases of TC for patients with symptomatology longer than 6 months, however it gave greater effectiveness to ESWT.(12) However, [name] et al, in 2014 published a randomized study which concluded that "ultrasound-guided needling treatment was more effective in restoring function and short-term pain relief." (13)

The aim and desire of this study goes a bit further and is outlined below.

3. Main and secondary objectives

1. Main objective:

- The main objective is to compare the mean differences in VAS at 1 month, 3 months and 6 months according to the treatment received, US-PICT or ESWT in patients with TC according to the evolutionary stage of the lesion based on the Bianchi Martinoli classification.

2. Secondary objectives:

- To know if there are variations in functionality with the Latinen test, joint balance (ROM), PGI and CGI.
- To protocolize an attitude towards this type of pathology.
- To favor the use of hospital resources.

4. Design of the study

Design: We propose to conduct a **prospective experimental longitudinal analytical block randomized clinical trial**.

Study population, variables and inclusion-exclusion criteria.

Inclusion criteria:

- Patients aged 30 - 60 years.
- Omoalgia lasting more than 3 months.

- Radiographic and ultrasound visualization in both planes of calcification.
- Sizes > 5 millimeters (mm).

Exclusion criteria:

- Patients not meeting inclusion criteria.
- Presence of another evident cause of pain (joint degeneration, capsulitis, rotator cuff tendon ruptures...).
- Patient who has previously received ESWT or US-PICT.
- Contraindication of therapies: infection, drug allergies, cancer....

Variables to take into account:

- Age: years
- Sex: male/female
- Type of therapy: ESWT/barbectomy
- Endocrine/rheumatologic diseases: hypothyroidism, diabetes mellitus and rheumatoid arthritis.
- Number of calcifications
- Size of calcifications: mm
- Previous treatments: Yes/ No
- Location of calcification: Supraspinatus, subscapularis, and infraspinatus.
- ROM: Flexion, abduction, and external and internal rotation (°).

- **Visual analgesic scale (VAS):** initial, at 1, 3 and 6 months.

- **Latineen test: initial, at 1, 3 and 6 months of each test variable and final score.**

Correlation of VAS levels and Latineen test: (14)

VAS of 0 - 2.5 → IL = 6 VAS of 2.5-5 → IL=10 VAS of 5-7.5 → IL 13 VAS of 7.5-10 → IL =14

- **Patient Global Impression of Improvement Scale (PGI-I)**
- **Global improvement impression scale (CGI - GI)**

Sample size

Accepting an alpha of 0.05 and a beta of 0.2 in a bilateral contrast, 28 subjects in each arm are required to detect a difference equal to or greater than 3 units on the VAS scale. A standard deviation of 5 is assumed. A loss-to-follow-up rate of 20% has been estimated.

Work plan

The protocol carried out was as follows:

1st Phase : in this first phase, patients will be collected according to the criteria set out above for a period of **12 months**. During this time, the patients will be explained the two possible treatments to be received and after signing the appropriate informed consent, **they will be divided into groups according to treatment (ESWT vs US-PICT) stratifying according to the Bianchi Martinoli classification: (I/II or III)**. The decision for each

treatment will be made randomly, **dividing the patients in a 1:1 ratio** according to whether they come to the initial consultation and the previous patient has received one or the other treatment.

The variables indicated above and in the table of variables will be collected from these patients.

	ESWT	US-PICT
Type I	14n	14n
Type II/III	14n	14n

In relation to **ESWT**, these will be given using a **15 mm transmitter in continuous mode with pressure at 3 bar, frequency 12Hz and 3000 impacts**. The number of sessions will be between 4 - 8 according to the patient's clinical condition with a rest between sessions of 5 to 10 days.

US-PICT will be performed with 1 session in which the following actions will be performed:

- First, a **suprascapular nerve block** will be performed with corticosteroid and anesthetic (3 ml of bupivacaine) in an ultrasound-guided manner.
- Then **the calcification will be infiltrated** with 5 ml of local lidocaine and preloaded physiological saline solution under ultrasound guidance.
- Finally, **repeated suctioning** with physiological saline will be performed to extract the calcium in an echoguided manner.

The inclusion of patients in the study will be carried out by [name]. The barbotomy technique will be performed jointly by [name], [name] and [name]. The ESWT technique will be performed by Fst. [name].

2nd Phase: Subsequently, 3 revisions will be carried out. One at 1 month, 3 months and another at 6 months after the end of therapy. In these, the variables will be taken again as indicated in the table of variables.

Initial consultation	1 month	3 month	6 month
Age Gender Type of therapy Diseases Number of calcifications Size Previous treatment Location ROM (measurement with goniometer) VAS _{in} Latineen Test	ROM (measurement with goniometer)	ROM (measurement with goniometer)	ROM (measurement with goniometer) VAS _{6m} Latineen Test PGI – I CGI - GI

Table of variables

3rd Phase: The information collected will be synthesized and entered into the SPSS program to obtain the results. For these the following actions will be carried out:

[figure not shown]
- For an independent data design:
 - 2 groups: Student's t-test or Mann-Whitney U-test.
 - More than 2 groups: Analysis of variance or Kruskal-Wallis "H" test.
- For a paired data design:
 - 2 groups: Student's t-test for paired data or Wilcoxon test.
 - More than two groups: Analysis of variance for repeated measures or Friedman's test.

A new variable VAS difference (VASDIF) will be created later, with the data obtained, according to the following formula in order to evaluate the variation with the initial VAS levels.

[figure not shown]
$$\text{VAS}_{\text{in}} - \text{VAS}_{\text{xm}} = \text{VASDIF}_{\text{xm}}$$

Main variables: VAS, Test de Latineen y variables, PGI y CGI.
 Variable agrupadora: ESWT Vs US-PICT

Type I calcifications

Type II/III calcifications

All contrasts will be bilateral and those where $P < 0.05$ will be considered significant. Data will be collected, processed and analyzed with SPSS v.21 statistical software.

Limitations of the study

In order to be able to carry out the following study, the following limitations can be found.

1. Poor adherence to the study by the patients causing losses.
2. Increased waiting times due to ESWT saturation.

Ethical aspects

It will be respected at all times, through data anonymity in the base by a person external to this project, the confidentiality of these, in accordance with Regulation (EU) 2016/679 of the European parliament and of the council of 27 April 2016 on the protection of natural persons with regard to the processing of personal data and on the free movement of such data (General Data Protection Regulation). Likewise, the project will be subject to the rules of good clinical practice and will comply at all times with the ethical precepts contained in the Helsinki declaration, always ensuring compliance with the organic law 3/2018 on the protection of personal data. With the ultimate aim of respecting and safeguarding the rights of privacy, image and information, accessing only and exclusively to information that is relevant to the study and separating the information so that it is not possible to identify patients.

The results obtained will be published through the normal channels of scientific dissemination, whatever the results obtained.

Resources required

The study will be carried out at the Physical Medicine and Rehabilitation Services of the Hospital Universitario Reina. Hospital resources will be necessary for the tests to be ordered.

The database will be created using the SPSS v.21 statistical program and the data will be obtained from the Diraya clinical database.

This study does not have any economic funding.

Bibliographic references.

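### The starting hypothesis asserts equal VAS change, but the plan has only two-sided difference tests and no rule for a non-significant result, which could be misread as confirming equality

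*Combined protocol and SAP*

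**What the plan says.** - **Hypothesis (section 1, Starting assumptions).** The only sentence labelled as a hypothesis says that US-PICT patients, across the degrees of the disease, "obtain the same VAS differences at 1 month, 3 months and 6 months as patients who received ESWT as treatment in the population".
- **Objective (section 3).** "The main objective is to compare the mean differences in VAS at 1 month, 3 months and 6 months according to the treatment received", by stage of the lesion. It contains no equivalence or non-inferiority wording.
- **Sample size (section 4).** "Accepting an alpha of 0.05 and a beta of 0.2 in a bilateral contrast", the plan states that "28 subjects in each arm are required to detect a difference equal to or greater than 3 units on the VAS scale". It adds "A standard deviation of 5 is assumed" and "A loss-to-follow-up rate of 20% has been estimated". The table in the Work plan puts 14 patients in each treatment-by-type cell.
- **Analysis (section 4, Work plan, 3rd Phase).** The between-group tests are Student's t or Mann-Whitney for two groups, and analysis of variance or Kruskal-Wallis for more. VASDIF is the baseline VAS minus the follow-up VAS. On decisions, the text says "All contrasts will be bilateral and those where" P is below 0.05 count as significant.

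The readable text has no equivalence margin, no confidence-interval criterion, and no statement of how P >= 0.05 will be interpreted.

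**The concern.** The hypothesis and the decision rule point in opposite directions. A two-sided difference test can reject equality. It cannot establish it. If the stated hypothesis is what the trial sets out to support, the only test outcome compatible with it is failure to reject, and that can come from imprecision as easily as from similar treatments.

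This matters because of how the results are to be used. Section 1 wants to know when each therapy should be indicated, and section 3 lists a treatment protocol among its aims. If an imprecise null result within a calcification type were reported as agreeing with the hypothesis, the two therapies would look interchangeable there without evidence for it.

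**Working it through.** **Inputs.** From Sample size: difference of interest 3 VAS points, SD 5, two-sided alpha 0.05, power 0.80, loss 20%. From the Work plan: 14 per cell, so 28 per arm. Assumption: the SD of 5 is the SD of VASDIF in each arm; the plan does not say which VAS quantity it describes.

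**The plan's own figure.** For two independent means, n per arm = 2 x [5 x (1.960 + 0.842) / 3]^2 = 43.6, so 44, and 44 / 0.8 = 55 with loss. The stated 28 is not reproduced. That is a separate sample-size problem. The sizes below are taken as planned.

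**Precision.** The expected 95% CI half-width for a difference in means is h = t(0.975, 2n - 2) x SD x sqrt(2/n).

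| Comparison | n per group | t | h at SD 5 | h at SD 2.5 (assumed) |
|---|---|---|---|---|
| Overall, planned | 28 | 2.005 | 2.68 | 1.34 |
| Overall, after 20% loss | 22 | 2.018 | 3.04 | 1.52 |
| Within a type, planned | 14 | 2.056 | 3.88 | 1.94 |
| Within a type, after 20% loss | 11 | 2.086 | 4.45 | 2.22 |

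The loss rows use 28 x 0.8 = 22.4 and 14 x 0.8 = 11.2, rounded down.

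**What a non-significant result would exclude.** With the t-test, P >= 0.05 means that the 95% CI contains 0, so the observed difference d satisfies |d| <= h. The CI excludes both +3 and -3 only if |d| + h < 3.

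- *14 v 14, SD 5:* h = 3.88 exceeds 3, so no value of d meets the condition. A CI that contains 0 and is 2 x 3.88 = 7.76 points wide must reach past +3 or -3. The observed SD would have to fall below 3 / (2.056 x sqrt(2/14)) = 3.86 before any result could exclude both. Hence "usually" and not "always".
- *28 v 28, SD 5:* both are excluded only if |d| < 3 - 2.68 = 0.32, whereas non-significance covers |d| up to 2.68.
- *14 v 14, SD 2.5:* both are excluded if |d| < 3 - 1.94 = 1.06, out of a non-significant range up to 1.94.
- *28 v 28, SD 2.5:* the CI reaches at most 2 x 1.34 = 2.68, so every non-significant result excludes 3 points. Smaller differences remain possible.

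**Could the 3-point figure serve as an equivalence margin?** It is stated as a difference to detect, with no argument that smaller differences are unimportant. Even if it were used, with SD 5 and a true difference of 0, the simulated chance that a 90% CI lies wholly within -3 to +3 is 43% at 28 per arm, 25% at 22, 4% at 14 v 14 and 1% at 11 v 11.

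**The case against.** **The sentence is simply a null hypothesis.** This is the strongest reply, and it is plausible. The objective is to compare, the sample size is for detection of a difference, the tests are two-sided, and equivalence is mentioned nowhere. The two-sided contrast to detect 3 points supplies an alternative in substance, so it would be too strong to say that the plan has none. What stands is that the sentence is presented as the research hypothesis, is not labelled H0, and has no companion rule for a non-significant result.

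**Nobody says that a null result will be called sameness.** Correct. A reader might infer that the sponsor intends to report P >= 0.05 as confirmation, but the documents never say how such a result will be interpreted. They support only "could be read", not "would be read".

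**The imprecision is another problem.** Largely so. With a true 3-point difference and SD 5, the t-test would miss it 40% of the time at 28 per arm and 67% at 14 v 14. Those rates come from the sample size, the split by type and the assumed SD, and rewording the hypothesis changes none of them. They should not be counted again here.

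**SD 5 is large for VAS bands that run from 0 to 10.** A fair point, which is why the results at 2.5 are shown. At that SD the overall comparison would exclude 3 points whenever it was non-significant. The within-type comparison still might not.

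**Something may be in the missing figures.** Two figures in the 3rd Phase text are not shown, so absence can be asserted only for the readable text.

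**Conclusion.** The point holds as a mismatch between the stated hypothesis and the decision rule, together with a missing rule for P >= 0.05. It does not show that the planned tests are wrong for a difference trial, or that the sponsor means to claim equivalence.

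Its size depends on the SD. At the plan's own value, a non-significant result within a type would usually not exclude the plan's own 3-point difference, and the overall comparison would exclude it only when the observed difference is close to zero. At the assumed SD of 2.5 the problem shrinks, but it remains within types. The figures also assume the t-test on VASDIF and the planned cell sizes.

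The matter should be settled before results are seen, because it decides what the trial may conclude. It does not invalidate the design.

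**What to change.** 1. In section 1, replace the hypothesis with H0: mean VASDIF is equal between arms, against H1: it is unequal. This matches the sample-size paragraph and the tests already listed.
2. In the 3rd Phase text, state that each between-arm difference in mean VASDIF, overall and by calcification type, will be reported with its 95% CI.
3. Add that P >= 0.05 will be reported as inconclusive and not as evidence that the treatments are the same.
4. Add that no equivalence claim will be made unless a clinically justified margin is prespecified. The 3-point difference to detect should not be reused as that margin.

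Items 1 to 3 need only wording: no new data, visits or patients. The downside is that some results the sponsor might call equal must be called inconclusive. A genuine equivalence aim would cost much more. For illustration only, even a margin as wide as 3 points at SD 5 would need 2 x [5 x (1.645 + 1.282) / 3]^2 = 47.6, so 48 per arm, or 48 / 0.8 = 60 with 20% loss (80% power, true difference 0, 90% CI), for a single overall comparison. The low power of the planned size should be dealt with under the sample-size calculation.

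### The objective and hypothesis define the groups by treatment received, and nothing in the plan commits to analysing patients in the arm they were allocated to

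*Combined protocol and SAP*

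**What the plan says.** The main objective (section 3) compares mean VAS differences at 1, 3 and 6 months "according to the treatment received, US-PICT or ESWT in patients with TC", by Bianchi Martinoli stage. The starting hypothesis (section 1) is worded the same way for both groups: those "who have received US-PICT as treatment" are expected to do the same "as patients who received ESWT as treatment in the population".

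The analysis text (section 4, 3rd Phase) gives the grouping only as "Variable agrupadora: ESWT Vs US-PICT", without saying allocated or received. The variable list has one field, "Type of therapy: ESWT/barbectomy". The table of variables places it at the initial consultation and at no later visit: "Age Gender Type of therapy Diseases Number of calcifications".

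The design is described as block randomised, 1:1. No section mentions intention-to-treat, per-protocol, an analysis set, or what happens to patients who do not start or who change treatment. ESWT takes 4 to 8 sessions, 5 to 10 days apart; US-PICT takes one. The listed limitations are losses from poor adherence and "Increased waiting times due to ESWT saturation".

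**The concern.** Randomisation makes the arms comparable as allocated. Grouping by what patients went on to receive keeps that protection only if departures from allocation are unrelated to outcome. Here the objective and hypothesis are the only text that defines the groups, and both say received.

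Departures are more likely on the ESWT side, because the course is long and a waiting list is foreseen. Three kinds would change the groups under a literal reading:

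- a patient allocated to ESWT who never starts;
- one who switches to US-PICT;
- one who is excluded from analysis.

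Visits are timed from the end of therapy, so a patient who never starts also has no defined follow-up date. With a single therapy field, a change of treatment may leave no record of both facts. If patients with a worse or better outlook depart preferentially, the test can show a difference where there is none, or hide one.

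**Working it through.** **The plan's own figure.** The only stated figure nearby is 28 per arm (difference 3, SD 5, two-sided alpha 0.05, beta 0.2, 20% loss). It does not reproduce for two independent arms: n = 2 × (1.960 + 0.842)² × 5² / 3² = 43.6, so 44 per arm, and 44 / 0.8 = 55 with loss. That is a separate matter. I use 28 and SD 5 here only because they are the plan's values.

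**Inputs from the documents.** 28 per arm; SD 5; target difference 3; two-sided 5% test.

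**Inputs assumed.** The documents give no switching rate and no link between departure and outcome. I take no true difference and 3 or 6 of 28 ESWT patients (nominally 10% and 20%) moving to US-PICT. The movers are those with the highest tendency to leave, which has correlation ρ with poor improvement.

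**Size of the bias.** Moving k of n patients whose mean VASDIF is lower by ρ × SD × m gives

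bias = ρ × SD × m × k × [1/(n + k) + 1/(n − k)],

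where m is the average of the k largest of 28 standard normal values (about 1.64 for k = 3 and 1.31 for k = 6).

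- k = 3: 3 × (1/31 + 1/25) = 0.217. Bias is 0.3 × 5 × 1.64 × 0.217 = 0.53 at ρ = 0.3, and 0.89 at ρ = 0.5.
- k = 6: 6 × (1/34 + 1/22) = 0.449. Bias is 0.3 × 5 × 1.31 × 0.449 = 0.88 at ρ = 0.3, and 1.47 at ρ = 0.5.

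**Simulation (20,000 trials per setting, t-test).** Bias is in VAS points in favour of ESWT, because poor responders are the ones assumed to leave it.

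| Switching | ρ | Bias | Type I error |
|---|---|---|---|
| 10% | 0 | 0 | 5.0% |
| 10% | 0.3 | 0.5 | 6.5% |
| 10% | 0.5 | 0.9 | 9.6% |
| 20% | 0 | 0 | 5.1% |
| 20% | 0.3 | 0.9 | 9.9% |
| 20% | 0.5 | 1.5 | 18.5% |

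Analysed as allocated, the same trials show no bias and an error of about 5%.

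If the leavers are dropped rather than moved, 20% departure gives a bias of 0.5 to 0.9 and an error of 6.7% to 10.3% for ρ = 0.3 to 0.5.

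**Sensitivity to SD.** The bias is proportional to SD, so at SD 2.5 it halves, to about 0.3-0.7 points. The error rate stays the same, because bias and standard error shrink together.

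**Cost of analysing as allocated.** If switchers take on the other treatment's full effect, a 3-point effect becomes 3 × (1 − s): 2.7 at 10% switching and 2.4 at 20%. The same formula then gives 54 and 69 per arm before loss, against 44.

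**The case against.** The strongest reply is that 'received' is loose wording and that the trial would be analysed by assigned arm anyway. There is evidence for this. Therapy type is recorded at the initial consultation, before a multi-session course, so the field may well hold the assigned treatment, and a later switch would not alter it. The work plan speaks of treatments to be received before anyone is allocated, and ties assignment to what the previous patient received, when that patient may still be mid-course. The plan nowhere contrasts received with allocated. This stands: a reader might infer that the sponsor has chosen an as-treated analysis and that the randomised comparison is therefore broken, but the documents do not show that. They show objective wording that reads as as-treated and an analysis population left undefined.

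A reader might also infer that patients who stop ESWT early disturb the groups. They do not: such a patient has received ESWT and stays in that group. Only never starting, switching or exclusion matters, and the plan describes no switching and no exclusion of non-completers.

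The magnitude is fairly challenged too. The switching rates and correlations are assumptions. The direction is not assured: the background section calls the disease self-limiting, so patients waiting for ESWT might leave because they have improved, which would reverse the sign.

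None of this supplies the missing commitment. If analysis by allocation is intended, the text says something else.

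**Conclusion.** The point holds as a gap to close. The objective and hypothesis, read literally, specify an as-treated comparison, and nothing elsewhere commits to analysis by allocated arm.

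The consequence is conditional. With one-way switching of 10-20%, a correlation with outcome of 0.3-0.5, SD 5 and 28 per arm, the bias is about 0.5-1.5 points against a target of 3, and the type I error about 7-18%. With departures unrelated to outcome there is no bias. These figures illustrate what could happen and do not predict the trial's error rate.

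Analysis by allocation would not cure selective loss to follow-up (20% is anticipated), nor an allocation rule that depends on the previous patient's treatment. Those are separate issues. I rate this as a change that should be made, with medium confidence.

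**What to change.** 1. In the main objective and the starting hypothesis, replace treatment received with treatment allocated.
2. In the analysis section, define the grouping variable as the allocated arm. State that every randomised patient with follow-up data is analysed in that arm and in the Bianchi Martinoli stratum used at randomisation, whatever treatment was started, completed or switched to.
3. Record allocated therapy and received therapy as two fields, and say how follow-up visits are dated for a patient who never starts.
4. Report the as-treated comparison only as a sensitivity analysis.

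The cost is a few wording changes and one extra data column. The statistical price is the dilution shown in the working, which is modest if switching is rare but not negligible at 20%. Restricting to patients with follow-up data leaves missing outcomes to be handled by a separate rule.

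### The stated inputs require 44–45 evaluable (55–57 enrolled) patients per arm, not 28; if SD 5 applies to the VAS change, 28 per arm gives about 60% power, not 80%

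*Combined protocol and SAP*

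**What the plan says.** The Sample size paragraph in section 4 opens "Accepting an alpha of 0.05 and a beta of 0.2 in a bilateral contrast" and concludes that "28 subjects in each arm are required to detect a difference equal to or greater than 3 units on the VAS scale". It then adds: "A standard deviation of 5 is assumed. A loss-to-follow-up rate of 20% has been estimated". It names no formula or test. It does not say which quantity has an SD of 5, where that value comes from, or whether 28 is the number before or after loss. The allocation table in the Work plan (1st Phase) uses 28 as the number allocated per arm, split into 14 per lesion-type cell.

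The analysis is described in the Work plan, 3rd Phase. For independent data it lists "2 groups: Student's t-test or Mann-Whitney U-test", with ESWT versus US-PICT as the grouping variable and results shown separately for type I and type II/III calcifications. The analysed quantity is a change from baseline: "A new variable VAS difference (VASDIF) will be created later". The main objective (section 3) compares the two treatments "in patients with TC according to the evolutionary stage of the lesion based on the Bianchi Martinoli classification". The starting hypothesis (section 1) is that US-PICT patients "obtain the same VAS differences at 1 month, 3 months and 6 months as patients who received ESWT".

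**The concern.** A difference of 3 with an SD of 5 is a standardised difference of 0.6. Two independent groups need well over 28 patients each to detect that with 80% power, even before any loss. So 28 does not follow from the inputs beside it.

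This is the plan's only justification of its size. If the SD is right, the trial is much weaker than stated, and weaker still within lesion type, where the main objective lies and no power is given. The starting hypothesis adds to the problem. A trial with little power is likely to give a non-significant result, which could be read as support for equal effects although the data would still allow a difference of about the size the trial was meant to detect.

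**Working it through.** **Inputs** (Sample size, section 4): difference 3; SD 5; two-sided alpha 0.05 (z = 1.960); beta 0.2 (z = 0.842); loss 20%. Allocation is 1:1 (Work plan, 1st Phase). The comparison is between two independent arms (section 3; Work plan, 3rd Phase). (1.960 + 0.842)² = 7.849.

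**Can 28 be reproduced?** Not for two independent arms.

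- Two-sided, normal formula: n = 2 × 7.849 × (5/3)² = 43.6, so 44 evaluable per arm. With loss: 44/0.8 = 55.
- Two-sided, noncentral t: power is 79.5% at 44 and 80.4% at 45, so 45. With loss: 45/0.8 = 56.25, so 57.
- One-sided, which the plan does not specify: 35 (normal) or 36 (t) before loss, still above 28.
- One-sample or paired normal formula: 7.849 × (5/3)² = 21.8; 21.8/0.8 = 27.3, so 28.

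Only the last route gives 28. It lacks the factor 2 for two independent groups and has the 20% loss built in. The one-sample t calculation gives 24, and 24/0.8 = 30, so the match holds only for the normal formula. As the plan names no formula, this is a possible origin and no more.

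**What the planned numbers deliver if 5 is the SD of the VAS change.** Evaluable numbers: 28 × 0.8 = 22.4, so 22; 14 × 0.8 = 11.2, so 11. The standard error of the difference is 5 × √(2/n). Power comes from the noncentral t with 2n − 2 degrees of freedom. The half-width of the 95% CI is the t quantile times the standard error.

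| n per group | t-test power for 3 points | Mann-Whitney power (simulated, normal data) | Difference detectable with 80% power | 95% CI half-width |
|---|---|---|---|---|
| 28 (arm) | 59.7% | about 57% | 3.8 | 2.68 |
| 22 (arm, after loss) | 49.4% | about 47% | 4.3 | 3.04 |
| 14 (cell) | 33.3% | about 31% | 5.5 | 3.88 |
| 11 (cell, after loss) | 26.8% | about 25% | 6.3 | 4.45 |

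The Mann-Whitney figures come from 20,000 simulated trials per size.

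**How far this depends on the SD.** The values below are assumptions, because the plan gives no source.

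| SD of change | 28 / 22 per arm | 14 / 11 per cell |
|---|---|---|
| 2.5 | 99 / 97% | 86 / 76% |
| 3 | 96 / 90% | 72 / 61% |
| 3.5 | 88 / 79% | 59 / 48% |
| 4 | 79 / 68% | 48 / 39% |

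Power of 80% for 3 points needs an SD of the change of about 3.9 (28 per arm) or 3.5 (22 per arm), and about 2.7 (14 per cell) or 2.4 (11 per cell).

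If 5 is instead the SD of the raw score at each visit, the SD of the change is 5 × √(2(1 − r)), where r is the correlation between baseline and follow-up. At assumed r of 0.3, 0.5, 0.7 and 0.8, power with 28 / 22 per arm is 46/38%, 60/49%, 81/71% and 94/87%. The VAS bands in the list of variables (section 4) run from 0 to 10. On that scale 5 is the largest possible population SD, reached only if half the patients score 0 and half score 10.

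**The case against.** The strongest objection is that the SD, not the number of patients, may be the wrong input. A value of 5 is hard to credit on a 0–10 scale. With an SD of the change of 2.5 to 3, the pooled comparison has 90–99% power with 22 to 28 per arm. What is shown is then a justification that cannot be reproduced, not a pooled comparison that is certainly underpowered. This stands, and it is why the power figures above are conditional. It does not rescue the paragraph: if 5 is wrong, the stated SD needs correcting instead. Within lesion type, even an SD of 3 gives only 72% (14) or 61% (11).

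A second objection is that SD 5 could refer to the raw score, in which case 28 evaluable per arm reaches 81% at a correlation of 0.7. That is true, but it needs the maximum possible raw SD together with a correlation the plan never states. After 20% loss the same case gives 71%.

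A third is that the sample-size sentence does not say the difference is between arms, and the plan also lists paired tests, for which 28 follows from the normal formula. That may well be how the figure arose. It would mean the trial was sized for change within an arm, whereas the main objective compares arms.

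Finally, the starting hypothesis may be no more than a null hypothesis, and nothing in the plan says that non-significance will be read as equality. That is fair: the misreading is a risk, not a stated intention.

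**Conclusion.** The concern holds. For the between-arm comparison in the plan, the stated inputs give 44–45 evaluable or 55–57 enrolled per arm, and 28 is wrong whether it is taken as before or after loss. If 5 is the SD of the analysed VAS change, power is about 60% with 28 and 49% with 22 evaluable, some 20 to 30 percentage points below the 80% stated. A true 3-point difference would be missed about 40% or 51% of the time, and the 95% CI would extend 2.7 to 3.0 points either side of the estimate.

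The mismatch needs no assumption beyond the plan's own inputs and two independent arms. The size of the power loss does depend on the SD, which the plan neither defines nor sources. The missing power statement within lesion type is a separate omission: 33% or 27% at SD 5. The sample-size paragraph must be corrected.

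**What to change.** Establish first which SD was meant. If 5 is the SD of the VAS change, keep the planned numbers and replace the sample-size sentence with what they deliver, for example:

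> With 28 patients allocated per arm (about 22 evaluable after 20% loss), an SD of 5 for the VAS change and two-sided alpha 0.05, a two-sample t-test has 60% (49%) power for a 3-point difference; the difference detectable with 80% power is 3.8 (4.3) points. Within each lesion type, with 14 (about 11 evaluable) per arm, power is 33% (27%) and the detectable difference is 5.5 (6.3) points.

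If 5 is not the SD of the VAS change, state the intended SD and its source and recalculate both the pooled and the by-type figures. The SD should not be chosen to make 28 come out.

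In either case, report the type-specific results as estimates with 95% CIs, and do not describe a non-significant difference as showing that the treatments give the same result.

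This is a change of wording and needs no extra patients; the cost is a less favourable stated power. Keeping 80% power at SD 5 would instead mean enrolling 55–57 per arm (110–114 in total, against 56 planned), and that would still power only the pooled comparison.
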